3.11 Study Treatment Discontinuation Criteria

A subject will receive the assigned study treatment (e.g., SL-172154 and PLD or SL-172154 and MIRV) until any of the following events occur during the study:

- Documented disease progression (radiological or clinical)
- A subject suffers an AE that, in the judgement of the investigator, Sponsor, or Medical Monitor, presents an unacceptable risk to the subject
- General or specific changes in the subject's condition (e.g., a significant intercurrent illness or complication) that, in the judgement of the investigator, are unacceptable for further administration of study treatment
- Subject decides to discontinue further study treatment
- Occurrence of pregnancy
- Significant non-compliance with protocol requirements
- Death
- Termination of the study by Sponsor

If one agent in the assigned regimen is permanently discontinued for any reason, at the investigator's discretion, the subject may continue to receive the other agent in the assigned regimen as monotherapy until meeting one of study treatment discontinuation criteria.

In the event of permanent discontinuation of all study treatment, subjects should be strongly encouraged to complete all scheduled assessments at the PTV and the SFU contacts.

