For all subjects in all cohorts, premedication as prophylaxis for IRR with dexamethasone (8 mg IV), an antipyretic and antihistamines should be administered at least 30 minutes prior to each SL-172154 administration. For dosage and schedule of prophylactic premedications, please see Section 5.1.1. For subjects enrolled to receive MIRV, premedication with an antipyretic, antihistamine, and dexamethasone will be administered at least 30 minutes prior to each MIRV administration as described in Section 5.3.2.1.

Throughout the treatment period for all subjects, an ongoing review of available safety data will be undertaken by a SMC as described in Section 7.8. All subjects (dose escalation and dose expansion) will receive SL-172154 administered with either PLD or MIRV until documented disease progression, unacceptable toxicity or intolerance, withdrawal of consent, or the subject meets other criteria for discontinuation (whichever occurs first) as defined in Section 3.1.1.

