- m. **Scans for Disease Assessment and CA-125:** Baseline tumor assessments are required for all subjects within 28 days prior to the first dose of study treatment. CA-125 should also be obtained at screening within 28 days of first dose of study treatment. Baseline and on-treatment tumor assessments for all tumor types by RECIST v1.1 should include CT with contrast of chest, abdomen, and pelvis and other known sites of disease at each time point. Bone scan, PET/CT, and/or MRI should be performed only if clinically indicated. Tumor assessments must be performed at screening and at the following intervals until radiologic disease progression: during the last week (Days 22 to predose on Day 29) of every 2 cycles/8 weeks \pm 1 week through Cycle 6, every 3 cycles/ 12 weeks \pm 1 week thereafter up to year 2, and then every 6 cycles/ 24 weeks \pm 1 week up to conclusion of the study. Subjects who discontinue study treatment for reasons other than disease progression (e.g., AE or withdrawal of consent) will be monitored for radiologic response until start of another anti-cancer therapy, disease progression, withdrawal of consent, or death. CA-125 should be measured to coincide with each scheduled radiographic tumor assessment as outlined above with the last required assessment for CA-125 performed at the PTV which occurs 30 days (\pm 7 days) after the last dose of study treatment. If there is more than one week delay in any cycle, please perform all the subsequent disease assessments per schedule in weeks.
- n. **SL-172154 Administration:** Subjects will be monitored prior to and during each SL-172154 infusion. SL-172154 should be administered according to the prescribed dosing schedule in Cycle 1 to align with the safety DLT assessment and sample (PK, ADA, etc.) collection schedules. Beginning on Cycle 2 Day 8, a window of \pm 2 days is allowed for scheduled dosing days for drug administration (NOTE: each dose must be administered at least 5 days apart from the previous dose). If the start of a subsequent cycle (e.g., Day 1) is delayed, the current cycle length is extended (e.g., the cycle lasts longer than 28 days). The doses of SL-172154 in that cycle are not delayed (e.g., administered on Day 8, 15).

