8. ANTI-TUMOR ACTIVITY ASSESSMENTS

Although the clinical benefit of SL-172154 has not yet been established, the intent of offering SL-172154 is to provide a possible therapeutic benefit, and thus the subject will be carefully monitored for tumor response and symptom relief in addition to safety and tolerability. For the purposes of this study, subjects should be evaluated for response as outlined in the SOA. All subjects who underwent the first post-baseline disease assessment at the 8-week (PLD Cohort) or

6-week (MIRV Cohort) time point or progress or die before the first post-baseline disease assessment will be considered evaluable for response.

Refer to the SOA (Section 6.1 and Section 6.2) and Section 6.11 for the schedule of disease assessments. More frequent disease assessments may be performed at the discretion of the investigator as clinically indicated. CA-125 levels should be measured concurrently with radiologic tumor assessments (Section 6.5.9.3) and reported in EDC however response determination will be solely based on radiologic assessment in this study.

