8.2 Criteria for Treatment Beyond Initial Progression

Subjects will be permitted to continue study treatment beyond initial progressive disease provided the subject does not have clinical symptoms of progression, is tolerating study treatment, has experienced no decline in their ECOG performance status and is gaining clinical benefit as assessed by the investigator. The subject must be made aware of the potential benefits and risks of continuing the study treatment in the setting of progressive disease by signing a separate written informed consent.

The subject may continue to be treated beyond disease progression until one of the following criteria is met:

- Develops clinical symptoms or signs such that the benefit-risk ratio of continuing therapy is no longer justified.
- Experiences rapid progressive disease with risk to vital organs or critical anatomical sites requiring urgent medical intervention.

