16.5.1 Evaluation of Response

Complete Response (CR): Disappearance of target and non-target lesions and normalization of tumor markers. Pathological lymph nodes must have short axis measures < 10 mm (Note: continue to record the measurement even if < 10 mm and considered CR). Residual lesions (other than nodes < 10 mm) thought to be non-malignant should be further investigated (by cytology, specialized imaging or other techniques as appropriate for individual cases) before CR can be accepted. Response should be confirmed in a subsequent scan \geq 4 weeks after the scan showing CR.

Partial Response (PR): At least a 30% decrease in the sum of the measures (longest diameters for tumor lesions and short axis measure for nodes) of target lesions, taking as reference the baseline sum of diameters. Non-target lesions must be non-progressive disease. Response should be confirmed in a subsequent scan \geq 4 weeks after the scan showing PR.

Stable Disease (SD): Neither sufficient shrinkage to qualify for PR nor sufficient increase to qualify for progressive disease, taking as reference the smallest sum diameters while on study. Documented at least once \geq 4 weeks from baseline.

Progressive Disease (PD): At least a 20% increase in the sum of diameters of measured lesions taking as references the smallest sum of diameters recorded on study (including baseline) AND an absolute increase of \geq 5 mm. Appearance of new lesions will also constitute progressive disease (including lesions in previously unassessed areas). In exceptional circumstances, unequivocal progression of non-target disease may be accepted as evidence of disease progression, where the overall tumor burden has increased sufficiently to merit discontinuation of treatment or where the tumor burden appears to have increased by at least 73% in volume. Modest increases in the size of one or more non-target lesions are NOT considered unequivocal progression. If the evidence of progressive disease is equivocal (target or non-target), treatment may continue until the next assessment, but if confirmed, the earlier date must be used.

An **Overall Response** assessment will be reported with **each protocol-specified timepoint** for a disease assessment. The following table provides a summary of the overall response status at each timepoint for subjects who have measurable disease at baseline.

Target Lesions	Non-target Lesions	New Lesions	Overall Response
CR	CR	No	CR
CR	Non-CR/non-PD	No	PR

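### Protocol 3.11 and SAP 3.4 end study treatment at documented progression without exception, Protocol 8.2 permits it to continue, and no tumor assessments are scheduled for subjects who continue

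*Protocol*

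**What the plan says.** Protocol 3.11 gives study treatment "until any of the following events occur during the study", and the first event listed is "Documented disease progression (radiological or clinical". The item carries no exception and no pointer to Section 8.2. The synopsis states the rule twice (Study Design and Treatment Schedules). Protocol 3.1 has all subjects treated "until documented disease progression, unacceptable toxicity or intolerance, withdrawal of consent" or another discontinuation criterion. SAP 3.4 reproduces the 3.11 list.

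Protocol 8.2 provides otherwise: "Subjects will be permitted to continue study treatment beyond initial progressive disease provided the subject does not have clinical symptoms of progression". It adds three conditions (treatment is tolerated, ECOG status has not declined, the investigator judges that there is benefit) and requires "signing a separate written informed consent". It then gives two stopping criteria of its own, one of which is rapid progression that threatens vital organs or critical sites.

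On imaging, the PLD schedule (6.1, footnote m) says "Tumor assessments must be performed at screening and at the following intervals until radiologic disease progression". The MIRV schedule (6.2, footnote o) and Section 6.11 end at the same point, and Section 8.1 ends at disease progression. Section 8 adds: "More frequent disease assessments may be performed at the discretion of the investigator as clinically indicated".

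**The concern.** For one kind of subject the protocol gives two answers. A site working from 3.11 stops treatment and has no reason to offer the separate consent. A site working from 8.2 may continue, and could then be recorded as deviating from 3.11: Section 14.4 counts any noncompliance with the protocol, and SAP 6.2 tabulates deviations.

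Two things are at stake. The first is monitoring. A subject kept on treatment under 8.2 has left the scan schedule, yet one of the criteria for stopping that subject is about how fast the disease is progressing. The second is the safety and exposure data. Both are anchored to the last dose, so their length depends on which section was followed. Adverse event incidence is a primary outcome measure.

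**Working it through.** The plan states no figure on this point, so the check sets the passages side by side and then applies the SAP's own duration formula to an illustration.

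**Where the two rules differ**

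| Situation | 3.11, synopsis, 3.1, SAP 3.4 | Other passage |
|---|---|---|
| Clinical progression | Treatment ends | 8.2 does not apply, because it requires no clinical symptoms of progression |
| Equivocal radiologic progression | Not addressed | Appendix 16.5.1: "If the evidence of progressive disease is equivocal (target or non-target), treatment may continue until the next assessment" |
| Unequivocal radiologic progression, no symptoms, 8.2 conditions met | Treatment ends | 8.2 permits continuation |

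Only the third row is a contradiction.

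**What is scheduled after radiologic progression**

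- Scans: none. Footnotes m and o and Section 6.11 stop at radiologic progression, and 8.1 at disease progression.
- CA-125: tied to the scans, apart from the post-treatment visit sample.
- Extra scans: allowed under Section 8 at the investigator's discretion, not required.

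**Which endpoints are exposed**

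- Best overall response, and so ORR, closes at the first PD or new therapy (SAP 7.1).
- DOR and PFS end at first documented progression or death (SAP 7.4, 7.5).
- Treatment duration runs from the first dose to the last dose plus a fixed number of days, unless death or data cutoff comes first (SAP 8.1.1).
- Adverse events are collected to 30 days after the last dose (SAP 8.3).

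The last two therefore move with any continuation.

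**Illustration**

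Assumptions: no delays, all doses given, progression found on the scheduled scan, two further cycles under 8.2, and neither death nor data cutoff intervening. First dose is Day 1, so Day 15 of cycle c falls on Day (c − 1) × cycle length + 15. SAP 8.1.1 adds 7 days to the last dose for MIRV, and 14 days for PLD when the last dose is on Day 15.

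MIRV regimen (21-day cycles), progression at the Week 12 scan:
- Stop: last dose C4D15 = 3 × 21 + 15 = Day 78. Duration (78 + 7) − 1 = 84 days. AE window to Day 78 + 30 = 108.
- Continue: last dose C6D15 = 5 × 21 + 15 = Day 120. Duration (120 + 7) − 1 = 126 days. AE window to Day 150.
- Difference: 42 days in each.

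PLD regimen (28-day cycles), progression at the Week 8 scan:
- Stop: last dose C2D15 = 28 + 15 = Day 43. Duration (43 + 14) − 1 = 56 days. AE window to Day 73.
- Continue: last dose C4D15 = 3 × 28 + 15 = Day 99. Duration (99 + 14) − 1 = 112 days. AE window to Day 129.
- Difference: 56 days in each.

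These are per-subject figures. The documents give no proportion of subjects who would continue, so no cohort-level effect can be computed.

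**The case against.** The best reply is that 8.2 is a specific exception to a general rule. It has its own title, entry conditions, consent and stopping criteria, and the consent makes continuation a deliberate, documented act. That is a natural reading, but no passage states it, and 3.1 and SAP 3.4 repeat the unqualified rule. It also leaves the gap in scheduled assessments untouched.

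Other parts of the reply stand and limit the point:

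- **Site variation would not vanish.** Continuation under 8.2 rests on the investigator's judgment of benefit, so similar subjects could be handled differently even under one clear rule.
- **Imaging is not ruled out.** A reader might infer that continuing subjects cannot be scanned. Section 8 allows discretionary scans, and physical examination, ECOG and laboratory tests continue in every cycle. What is missing is a required scan.
- **Post-progression treatment is not invisible in the SAP.** A reader might infer that exposure before and after progression is never distinguished. SAP 8.1.1 marks the first PD on the per-subject duration plot. Only a tabular split of exposure and a split of adverse events are absent.
- **The extent is unknown.** A reader might infer that most of the roughly 102 subjects are affected, because median PFS on single-agent PLD is quoted as 2.1 to 3.7 months. That figure relates to about 12 + 14 = 26 planned subjects. The other 12 + 64 = 76 are in the MIRV cohorts, for which no median PFS is given. Progressing is also not the same as meeting the 8.2 conditions.

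Counting all adverse events to 30 days after the last dose is a coherent on-treatment definition, and there is no randomized comparison to bias. Splitting events at progression is therefore a preference, not a correction.

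**Conclusion.** The contradiction is in the current text of both documents. It is confined to unequivocal radiologic progression in a subject without clinical symptoms who meets the 8.2 conditions. For that subject the plan both ends and permits treatment and, if treatment continues, schedules no tumor assessment.

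The consequence is for conduct, safety monitoring and the length of exposure and adverse event follow-up. A reader might infer that the response and progression results are compromised. The documents do not support that, because ORR, DOR and PFS close at first progression. Under the illustration's assumptions, two extra cycles lengthen an individual's treatment duration and AE window by 42 days (MIRV) or 56 days (PLD). The number of subjects affected is not stated.

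The passages should be reconciled. Which clinical rule applies is for the sponsor.

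**What to change.** 1. Reconcile Protocol 3.11, the synopsis, Protocol 3.1 and SAP 3.4 with Protocol 8.2, so that one rule governs treatment after first RECIST progression. The sponsor decides which.
2. If continuation stays possible, cite 8.2 as an exception in 3.11 and SAP 3.4. State in footnotes m (6.1) and o (6.2), Section 6.11 and Section 8.1 which disease assessments apply while dosing continues.
3. Optionally, flag subjects treated beyond progression and summarize separately their exposure and TEAEs from the first dose given after PD. A cut at PD plus 30 days would not do this: 30 days exceeds a full 21- or 28-day cycle, so events from post-progression dosing would be counted as before progression.

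Items 1 and 2 cost amendment wording and a matching SAP edit, plus any scans the sponsor chooses to require. Item 3 costs one extra cut of tables built from dose, adverse event and progression dates already collected.

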3.12 Duration of Follow-Up

Subjects who are withdrawn from study treatment for unacceptable AE(s) should be followed until the event(s) are resolved, the subject is lost to follow-up, the AE is otherwise explained, or further recovery is not deemed to be feasible. Data on these events should be collected on the AE electronic case report form (eCRF).

Subjects who permanently discontinue study treatment for reasons other than progression will continue with disease assessments until progression or start of another anti-cancer therapy.

Subjects who discontinue study treatment for any reason other than withdrawal of consent will be followed for survival and will be contacted approximately every 3 months from PTV until death or the end of the study, whichever occurs first. During Survival Follow-up, the start date of the first anticancer therapy will be collected and entered in the electronic data capture (EDC) system.

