6.11 Assessment of Anti-Tumor Activity

The primary analysis of anti-tumor activity will be assessed according to RECIST v1.1 for solid tumors using CT with contrast of chest, abdomen, and pelvis and other known sites of disease. Bone scan, positron emission tomography (PET)/CT, and/or MRI should be performed only if clinically indicated. Tumor assessments must be performed at screening and at the following intervals until radiologic disease progression:

- SL-172154 + PLD: during the last week (Day 22 to predose on Day 29) of every 2 cycles/ 8 weeks±1 week through Cycle 6, and every 3 cycles/ 12 weeks ±1 week thereafter up to year 2 and then every 6 cycles/ 24 weeks ±1 week up to study conclusion. If there is more than one week delay in any cycle, please perform all the subsequent disease assessments per schedule in weeks.
- SL-172154 + MIRV: during the last week (Day 16 to predose on Day 22) of every 2 cycles / 6 weeks±1 week through Cycle 18, and every 3 cycles/ 9 weeks±1 week thereafter through Cycle 27, and every 4 cycles/ 12 weeks±1 week until study conclusion. If there is more than one week delay in any cycle, please perform all the subsequent disease assessments per schedule in weeks.

Refer to Section 8 for additional details.

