8.1 Disease Assessment

Imaging studies, preferably by contrasted computed tomography scan, for disease assessment of chest, abdomen and pelvis and all other sites of known disease will be performed at baseline and at the following intervals until disease progression as described in Section 6.11.

PET-CT, MRI, and/or bone scan should be performed as clinically indicated. The same imaging modality used at baseline should be employed subsequently. All post-baseline assessments require imaging of disease sites identified by baseline scans. Confirmatory scans should be performed at least 4 weeks (> 28 days) after initial documentation of an objective response. Contrast enhanced imaging is required unless the subject is precluded from receiving contrast (e.g., hypersensitivity, renal impairment).

If study treatment is withdrawn for reasons other than disease progression, radiographic disease assessments should continue as per the SOA until documented disease progression, the start of new anti-cancer therapy, withdrawal of consent or death.

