7.5 Progression Free Survival

The PFS based on RECIST 1.1 is defined as time from the first day of treatment to the first documented disease progression per RECIST 1.1 or death from any cause, whichever occurs first. Subjects who have not progressed at the time of analysis will be censored at the date of their last evaluable disease assessment. Subjects who start new anticancer therapy prior to the documented PD will be censored at the last evaluable disease assessment prior to the start of new anticancer therapy. The censoring guidance and the date of PD/death or censoring are given in the Table 8 below.

Table 8 Summary of Censoring Guidelines for PFS based on RECIST1.1

Situation	Date of PD/Death or Censoring	PFS Outcome
Documented PD or death from any cause	Date of the PD or death, whichever comes first	Event (unless the censoring rule specified below is met)
Start new anticancer therapy before documented PD	Date of last evaluable disease assessment prior to the start of new anticancer therapy	Censored
Death or PD immediately after ≥ 2 consecutive missed or non-evaluable disease assessments ¹ as per the protocol specified assessment schedule	Date of last evaluable disease assessment prior to missed or non-evaluable assessments, or the first dose of investigational product, whichever occurred last	Censored
No PD or death at time of analysis or lost to follow-up	Date of last evaluable post-baseline disease assessment	Censored
(No baseline disease assessment OR no post-baseline disease assessment) AND no death	Date of first dose with a duration of 1 day	Censored

¹ Two or more consecutive disease assessments derivation is based on the disease assessment schedule in Section 6 of the protocol for each treatment regimen (SL-172154 + PLD and SL-172154 + MIRV), with a one-week visit window considered. If a subject has two or more consecutive missed or non-evaluable assessments followed by an assessment showing no radiologic disease progression, then the assumption will be that the subject did not progress during the missed or non-evaluable assessments.

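### The protocol conflicts on whether scans continue after treatment stops for clinical progression; if they stop, RECIST-only PFS and DOR can be biased upward by informative censoring

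*Protocol*

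**What the plan says.** **Stopping treatment.** Protocol Section 3.11, repeated in SAP Section 3.4, opens its list of stopping reasons with "Documented disease progression (radiological or clinical", so either kind of progression ends treatment.

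**Scanning after treatment stops.**
- Protocol 3.12: "Subjects who permanently discontinue study treatment for reasons other than progression will continue with disease assessments until progression or start of another anti-cancer therapy." SAP 3.5 repeats it.
- Protocol 6.1 footnote m (PLD), with the same sentence in 6.2 footnote o (MIRV): "Subjects who discontinue study treatment for reasons other than disease progression (e.g., AE or withdrawal of consent) will be monitored for radiologic response".
- Protocol 8.1: "If study treatment is withdrawn for reasons other than disease progression, radiographic disease assessments should continue as per the SOA until documented disease progression". SAP Section 7 repeats it.

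None of these limits progression, as the reason for stopping, to radiologic progression.

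**The competing instruction.** Protocol 6.11: "Tumor assessments must be performed at screening and at the following intervals until radiologic disease progression". Footnotes m and o contain this requirement too, just before the sentence quoted from them above.

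**The endpoints.** SAP 7.5 ends PFS at "first documented disease progression per RECIST 1.1 or death from any cause, whichever occurs first". It adds: "Subjects who have not progressed at the time of analysis will be censored at the date of their last evaluable disease assessment." Table 8 also censors at the last evaluable scan when new therapy precedes documented PD, and when death or PD follows two or more consecutive missed or non-evaluable assessments. A living subject with no post-baseline scan is censored on day 1. SAP 7.4 applies the same rules to DOR. SAP 7.1 says clinical deterioration is not documented progression for best overall response.

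**The concern.** A subject who is failing clinically, but whose scans have not met RECIST PD, falls between the two sets of rules. If her scans stop, death is the only PFS event left to her, and Table 8 can remove that as well. Censoring then depends on the outcome: those who leave the risk set are known to be doing badly, while Kaplan-Meier assumes they fare like those who remain.

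The plan expects such subjects. The Response-Evaluable population (Protocol 9.2.1, SAP Section 4) includes subjects who stopped for progression before any post-baseline disease assessment, and that progression is most naturally clinical. Such a subject enters the ORR denominator without a response, yet if alive she adds one censored day to PFS.

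Each regimen is a single arm, so no concurrent control shares the bias. PFS and DOR are secondary outcomes, and preliminary efficacy informs whether a regimen goes on to Phase 2 (Protocol 3.4). The SAP has no sensitivity analysis for this.

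**Working it through.** The plan gives no figure to reproduce: no sample size, power or threshold rests on PFS or DOR. The check is a trace through the rules, then an illustration of size.

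**Trace.** Take a subject who stops for clinical progression without RECIST PD, at a site that follows 3.12.
1. Alive, no new therapy: censored at the last evaluable scan, or on day 1 if she has no post-baseline scan.
2. New therapy before PD: censored at the last evaluable scan before it, even if she later dies.
3. Death after two or more missed scans: censored back to the last evaluable scan or first dose, if the unscheduled scans count as missed.
4. Death before two missed scans, no new therapy: a PFS event, dated later than the clinical failure.

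At a site that follows 6.11, scans go on and RECIST PD can still be recorded.

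**Closed form.** With exponential PFS, if a share f of failures is censored rather than counted, the estimated hazard is (1 − f) times the true one, so the median is multiplied by 1/(1 − f). From 3.5 months (the middle of the protocol's 3 to 4 months):
- f = 10%: 3.5/0.9 = 3.89
- f = 20%: 3.5/0.8 = 4.38
- f = 30%: 3.5/0.7 = 5.00

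**Simulation.** 40,000 subjects per scenario, true median 3.5 months, the protocol's scan calendars and the Table 8 rules. The scans of clinical progressors stop. The comparator counts clinical progression as an event on its date. Assumed, not in the documents: f; median survival after progression of 3 months with no new therapy (A), 6 months with 30% starting new therapy (B), or 6 months with 60% (C).

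Six-month PFS, comparator → as written:

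| Regimen, f | A | B | C |
|---|---|---|---|
| PLD 10% | 33.0 → 35.2 | 33.0 → 36.1 | 33.2 → 36.5 |
| PLD 20% | 33.0 → 37.6 | 33.1 → 39.4 | 32.7 → 39.6 |
| PLD 30% | 32.4 → 39.4 | 32.3 → 42.3 | 32.6 → 43.5 |
| MIRV 10% | 33.2 → 35.6 | 33.7 → 36.9 | 33.7 → 37.1 |
| MIRV 20% | 32.6 → 37.7 | 32.9 → 39.7 | 33.0 → 40.2 |
| MIRV 30% | 32.5 → 40.3 | 32.5 → 43.1 | 32.6 → 43.9 |

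The differences run from 35.2 − 33.0 = 2.2 to 43.9 − 32.6 = 11.3 points. At f = 5% they are 1 to 2 points. Between 9% and 55% of clinical progressors still count as events under step 4.

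**Four months.** Other assumptions: true median 3.7 months (top of the protocol's PLD range), half of clinical progressors start new therapy, median post-progression survival 8 months. At f = 10%, 20% and 30%, PLD goes from about 50% to 53%, 56% and 59%. MIRV goes from about 58%, 57% and 55% to 62%, 64% and 67%, with the last at the top of the range.

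**Median.** The simulated median moves in jumps. At f = 10% MIRV stays at 4.14 months, while PLD goes from 3.68 to between 4.04 and 5.09. The closed form gives a smooth shift of 3.89 − 3.50 = 0.39 months. Much of the jump reflects where the scans fall, because the PLD curve lies close to 50% at the 16-week scan.

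**Effect of the wording change alone.** Same four-month assumptions, PLD, f = 20%, new therapy starting before the next scan: as written about 56%, with scans continued about 53%, comparator about 50%. So (53 − 50)/(56 − 50), about half the shift, remains, because subjects who start new therapy are still censored.

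**The case against.** The strongest reply is that 6.11 is mandatory and specific to radiologic progression, 8.1 takes its intervals from 6.11, and 3.12 says who continues without saying that anyone stops. The PLD schedule also marks a disease assessment at the post-treatment visit, and Section 8 allows extra scans when clinically indicated; either could catch RECIST PD near the time of stopping. The simulation includes neither. This stands. A reader might infer that scans do end for these subjects, that all of them are censored, and that PFS and DOR are overstated. The documents do not support that: the scan rule is a conflict, early deaths without new therapy remain events, and the rate of clinical-only progression is not given.

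Censoring of late deaths is itself open to argument: if scans were no longer required, perhaps none was missed. Table 8's footnote derives missed assessments from the protocol schedule, which leaves the point unsettled.

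RECIST-only events are a deliberate and consistent choice, and the endpoints are descriptive. Precision is low: with 20 PLD subjects the 95% half-width at 50% is 1.96 × √(0.25/20) = 22 points; with 70 MIRV subjects it is 1.96 × √(0.25/70) = 12. A shift of a few points may not change a decision. That limits the severity, but a bias in a known direction that is cheap to remove is still worth removing. Finally, the comparator is a different endpoint from RECIST PFS, so the figures do not measure what the wording change alone would gain.

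**Conclusion.** The concern holds as a conflict to reconcile. Protocol 3.12 and 8.1, part of footnotes m and o, and SAP 3.5 and 7 point one way; 6.11 and the rest of those footnotes point the other. Where sites follow 3.12, PFS and DOR can be biased upward, because failing subjects without RECIST PD are censored unless they die early without new therapy.

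The true size is unknown. The range of roughly 2 to 11 points in 4- to 6-month PFS rests on an assumed clinical share of 10% to 30%, exponential progression, assumed survival and new-therapy rates, and no scan at the time of stopping. The median shift is largely an artefact of the scan grid and should not be used as a headline. DOR was not simulated; its direction follows from SAP 7.4 using the PFS censoring rules. No power or error rate is affected. The change is a worthwhile, inexpensive improvement and does not challenge the design.

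**What to change.** 1. **Protocol 3.12, 8.1, 6.1 footnote m and 6.2 footnote o; SAP 3.5 and 7.** Align these with 6.11: scheduled scans continue, where feasible, until RECIST 1.1 radiologic progression, new anti-cancer therapy, withdrawal of consent or death, including after treatment stopped for clinical progression.
2. **SAP 7.4 and 7.5.** Keep the RECIST-only definition as primary. Add one supplementary PFS/DOR analysis that counts treatment discontinuation for clinical progression as an event on its date, and report how many subjects it affects. This part is needed because the wording change leaves subjects who start new therapy censored.
3. **First confirm the data.** Section 3.11 puts both kinds of progression in one item, and SAP 6.1 summarises only a primary reason for discontinuation. Check that the form separates clinical from radiologic progression and dates it; if not, a field must be added.

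The cost is wording in six places, continued scheduled scans for some subjects who are unwell, one extra analysis, possibly a form change, and PFS and DOR that may look less favourable.
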